4.2 Primary and Secondary Safety Endpoints

No safety endpoints are included.

5.0 STUDY INTERVENTION/INVESTIGATIONAL AGENT

5.1 Description

The intervention being tested is a tailored adherence-promotion intervention.

Intervention Dose and Duration: AYAs in the intervention group will participate in 4 bi-weekly intervention sessions (1 every other week over 8 weeks). These sessions are estimated to last 30-45 minutes each. On alternating weeks, AYAs will receive a text message check-in from the interventionist. An 8 week duration was selected to mirror the amount of time over which adherence naturally declines, is short enough to be completed during the prescribed oral medication regimen of most AYAs with cancer, and is consistent with the “couple of months” duration preferred by AYAs in our preliminary studies.

Intervention Session Content: During the intervention sessions, each AYA will receive modules of behavior change techniques (BCTs) tailored to their individual barriers. Intervention content (BCTs) will be tailored to each AYA's barriers via a 4-step tailoring process. First, AYAs randomized to the intervention condition will complete a barriers tool. Second, the barriers tool will generate a list of the AYA's top 3 barriers, which will be sent to the interventionist. Third, in the first session, the interventionist will review the list and engage in shared decision-making with the AYA to determine which of the 3 barriers the AYA would like to target. Fourth, following a standardized tailoring algorithm (see Fig 2), the interventionist will select and deliver the module of BCTs matched to this barrier during Sessions 1 and 2. As barriers are likely to change over time, the AYA will complete the barriers tool a second time prior to Session 3 and the AYA and interventionist will again engage in shared decision-making to choose the barrier to be targeted in Sessions 3 and 4.

Figure 2 summarizes the tailoring algorithm and content. When the barrier in column 1 is selected as the intervention target, the interventionist will deliver the BCT(s) in column 2. Each BCT represents a component of a health behavior change intervention that has been standardized via expert consensus and over 10 years of empirical research as published in the Theory and Techniques Tool

(<https://theoryandtechniquetool.humanbehaviourchange.org/tool>). The study protocol will include the full definition of each BCT per the Theory and Techniques Tool and include examples relevant to AYA cancer to help guide the interventionist (e.g., "Prompts/cues" = "Introduce or define environmental or social stimulus with the purpose of prompting or cueing behavior. The prompt or cue would normally occur at the time or place of performance. Examples: Help the AYA to set an alarm for when their doses are due").

	Barriers	BCTs
Capabilities	Knowledge of how/when to take it	Instruction on how to perform behavior
	Forget to take it	Prompts/cues; Problem-solving; Associative learning (e.g., pairing w activity)
	Don't realize when I run out	Problem-solving; Prompts/cues; Conserving mental resources (e.g. auto refills)
	Hard to time with meals	Instruction on how to perform behavior; Problem-solving
	Too many pills to take	Problem-solving
	Not home when doses due	Problem-solving; Restructure environment; Prompts/cues
	Don't like taking in front of others	Restructure social environment; Info about others' approval
	Don't like the taste	Adding objects to environment (e.g., gel capsule, food to mask taste)
	Hard to swallow	Graded tasks; Behavioral practice/rehearsal; Verbal persuasion
	Don't like the side effects	Instruction on how to perform behavior (discuss with team)
Opportunities	Hard to get refills	Prompts/cues; Practical social support; Restructure environment
	Can't afford it	Practical social support (e.g., consult with social worker)
	Don't get enough help	Practical social support; Social reward
	Tired of taking medication	Pros and cons; Goal setting; Incentives/rewards
	Don't feel like taking it	Pros and cons; Goal setting; Incentives/rewards
	It's inconvenient	Focus on past successes; Problem-solving
	Gets in the way of activities	Focus on past successes; Problem-solving
	Doesn't matter if I take it	Information about consequences; Pros and cons; Incentives/rewards

Fig 2. Barriers and Behavior Change Techniques (BCTs)

Text Check-Ins: On alternating weeks, the interventionist will check-in with the AYA via a text message including the AYA's target barrier, BCTs, and adherence calendar. The AYA may respond to obtain additional support on how to implement the BCTs if desired.

6.0 PROCEDURES INVOLVED

6.1 Study Design

This is a multisite feasibility pilot RCT that includes 4 sets of study procedures: 1) electronic monitoring of medication adherence; 2) intervention or control group participation; 3) self-report measure completion; and 4) an electronic medical record review (Fig. 3). Reminders (and thank you messages) for completing study procedures may be provided via text, email, and/or phone as preferred by the AYA.

6.2 Study Procedures

6.2.a. Electronic Monitoring of Medication Adherence. In this study, medication adherence will be monitored using an electronic pill bottle. The electronic pill bottle includes a computer chip in the cap that records a date- and time-stamp of each time the bottle is opened, our proxy for medication-taking behavior.

To be eligible for the study, AYAs must demonstrate < 95% adherence and use the electronic monitor without difficulty. A 4-week run-in period is included to assess these eligibility criteria. After an AYA is enrolled, they will receive an electronic monitoring device and be asked to store their eligible oral medication in this device for the duration of their participation in the study. AYAs who demonstrate ≥ 95% adherence during the 4-week run-in period and/or who have difficulty using the electronic monitoring device will be informed that they do not meet the eligibility criteria and their study participation will be ended at that point. AYAs with < 95% run-in adherence will continue with study procedures per Fig. 3 and be asked to continue to use the electronic adherence monitoring device until the end of the 4-week post-intervention period (for 17 total weeks).

Electronic Monitoring Device Distribution: AYAs will either be provided an electronic monitoring device at their recruitment visit or mailed an electronic monitoring device and provided instructions by a member of the CCHMC research team.

For participants currently enrolled in an ongoing clinical initiative including electronic adherence monitoring, adherence data will be downloaded from the clinic-provided device. Doing so will ensure that participants are only provided with one electronic monitor.

Electronic Monitoring Device Return: Participants will be asked to return their adherence electronic monitoring device at the conclusion of their participation in the study. In instances where participants are unable to bring their adherence electronic monitoring device to a study visit, a pre-paid addressed envelope will be provided so participants can mail their devices to the study team.

Cellular Phones: AYAs will be asked to download a mobile application to their personal cellular phone that they will use to upload data from their electronic monitoring device to a secure Cloud-based application (CertiScan® Cloud). If AYAs would not be able to participate in the study because they do not have access to an appropriate mobile phone (phone with NFC capabilities) and/or a data package, they will be given a CCHMC-provided cellular phone to use for the duration of the study.

6.2.b. Intervention or Control Group Participation. AYAs randomized to the intervention group (tailored adherence-promotion intervention, termed “Tailored Program”) will participate in 4 bi-weekly sessions with an interventionist and receive text check-ins on alternating weeks (see Section 5). AYAs randomized to the control group (uniform standard of care condition, termed “Feedback Program”) will receive a weekly text message

[figure not shown]

Fig 3. RCT Procedures

Cal + Con = Adherence calendar + contact information for medical team

from the interventionist including a calendar depicting their adherence and a medical team contact should they desire support (Fig 3).

Intervention sessions will be delivered via a HIPAA-compliant videoconferencing system (Zoom for Healthcare) or phone should technical difficulties arise with Zoom. All intervention sessions will be recorded.

6.2.c. Self-Report Measure Completion.

AYAs will complete pre- and post-treatment assessments remotely via REDCap, a secure, HIPAA-compliant web-based platform. Prior to use, the PI will test the online measures. The consent forms signed by all participants will detail the use of online measures. The self-report measures are summarized in Table 3. Published and validated versions of all measures will be used unless noted in Table 3.

Table 3. Self-Report Measures		
Domain	Measures Completed by AYAs, Psychometrics	Pre- Post-
Usability	System Usability Scale (SUS)³⁹ 10-item rating of usability, $\alpha=.91^{39}$	X
	System Usability Scale Adjective Rating⁴⁰ 1-item rating of user-friendliness, $r=.82$ w SUS ⁴⁰	X
Acceptability	Acceptability &Adherence Scale⁴¹ 7-item rating of psychological treatment acceptability (adapted from the Treatment Acceptability & Adherence Scale, $\alpha=.88^{41,42}$)	X
	3 Open-Ended Questions regarding potential refinements (see Table 2)	X
Refinements	Consultation and Relational Empathy (CARE) Measure 10-item rating of rapport and empathy, $\alpha=.93^{50}$	X
	Barriers Measure 18-item measure of barriers to adherence	X X
Preliminary Efficacy	Medical Adherence Measure⁴³ 2-item report of N missed and late doses, $r=.4$ with monitor ⁴⁴	X X
	Demographics – Self-reported Demographics Parental Involvement – Allocation of Treatment Responsibility, $\alpha=.85^{45}$	X
Control Covariates	Emotional Distress – Pediatric (ages 15-17) or Adult (ages 18-24) PROMIS Depression and PROMIS Anxiety Short Forms, $\alpha=.84-.86^{46,47}$	X

6.2.d. Chart Review. Medical diagnoses, date of cancer diagnosis, current medical regimen, cancer status (e.g., relapse), cancer-related complications, and health care utilization will be obtained via medical chart review. Trained study staff will conduct chart reviews.

6.3 Blinding. Participants will be blinded to the study hypotheses in that they will not be told that we expect the “Tailored Program” (intervention condition) to result in greater improvements in adherence (Exploratory Aim 2) than the “Feedback Program” (control condition). [name] (PI) will not be blinded as she will be providing clinical supervision to the study interventionist.

6.4 Procedures Conducted by Collaborating Site Staff. Study staff at collaborating sites will have 3 main responsibilities: 1) recruiting patients per the procedures described in Section 13; 2) conducting weekly medical record reviews to provide updates to the patient’s medical regimen (to allow for adherence data to be adjusted according to medication holds, etc.); and 3) assisting with a medical record review at the end of the study to obtain the information detailed in 6.2.d. Once a participant is recruited, their information will be securely transferred to CCHMC (as per 13.1) and CCHMC staff will oversee all other procedures as detailed in 6.5.

6.5 Procedures Conducted by CCHMC Staff. CCHMC staff will be responsible for enrolling CCHMC patients. CCHMC staff will also be responsible for: 1) assigning participants to the intervention or control condition; 2) delivering the intervention or control condition (i.e., distributing electronic adherence monitoring devices and cellular phones as necessary); 3) providing supervision to the coach delivering the intervention or control condition; 4) tracking participants’ progress; 5) overseeing adherence data collection and synthesis with data from weekly electronic medical record reviews; 6) administering and overseeing pre- and post-treatment

assessment visits; 7) managing all study data; 8) managing participant compensation; and 9) conducting data analyses. Each of these tasks will be detailed in our Standard Operating Procedures.

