2.0 OBJECTIVES

The purpose of this study is to conduct a pilot feasibility trial of a tailored adherence-promotion intervention as compared to uniform standard of care. This goal will be achieved via the following aims:

Aim 1: Conduct a feasibility pilot RCT of a tailored adherence-promotion intervention as compared to uniform standard of care including 40 AYAs with cancer (n = 20 per arm).

Hypothesis 1a: The intervention will meet enrollment, retention, fidelity, and data completion feasibility criteria.

Hypothesis 1b: AYAs will rate the intervention as easy to use and acceptable.

Exploratory Aim 2: To explore group differences in improvements in electronically-monitored medication adherence to inform the next phases of intervention development and testing.

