3.2 Preliminary Data Informing the Proposed Study Design

With support of her NCI K07, [name] is conducting a longitudinal observational study to identify predictors of medication adherence among AYAs (15-24 years) with cancer. Defining adherence as $\geq 95\%$ of prescribed doses taken, the threshold associated with a lower risk of relapse in acute lymphoblastic leukemia,⁷ our preliminary data indicate that 71% of AYAs are non-adherent per electronic monitoring data. This rate of non-adherence may be due to barriers faced by AYAs. At baseline, 90% of AYAs reported ≥ 1 barrier and a greater number of barriers was associated with lower electronically monitored ($r = -.49, p = .01$) and self-reported ($r = -.41, p = .01$) adherence. These data suggest that targeting barriers has the potential to improve adherence. Doing so, however, is complicated by the individual variability inherent in barriers. Of the 54 AYAs reporting barriers, only 10 reported the same barriers. The other 81% reported a different set of barriers than any of their peers. In addition, only 26% endorsed forgetting and/or lack of knowledge, the barriers targeted by previous interventions.^{24,34,35} Because most AYAs have unique barriers, it is not surprising that “one-size-fits-all” interventions targeting barriers endorsed by only some AYAs demonstrate limited efficacy.^{24,34,35} Instead, our data suggest that delivering BCTs tailored to an AYA’s top barriers may improve adherence.

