9.0 STUDY TIMELINE

9.1 Subject Participation Duration

Adolescents and young adults enrolled in this study will participate in a 4-week run-in period, 1 week pre-treatment assessment, 8-week intervention or control group, and 4 week post-treatment period. In all, the estimated duration of subject participation is 17 weeks.

Given the demanding nature of cancer treatment, all study procedures can be completed +/- 2 weeks of the planned completion date and still be considered completed "on time."

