	System Usability Scale Adjective Rating ⁴¹	Mean score of AYAs randomized to treatment group	M ≥ 4 ⁴¹
Acceptability (Hyp 1b)	Acceptability &Adherence Scale ⁴²	Mean score of AYAs randomized to treatment group	M ≥ 28 ⁴³

Data from the open-ended refinement questions (see Table 2) will be coded in NVivo by two independent raters using theoretical thematic analysis, a method selected as it codes for themes related to specific research questions such as those posed in this grant (i.e., “What could we change about the intervention to make it more acceptable to AYAs?”).

Exploratory Aim 2: To explore group differences in improvements in electronically-monitored medication adherence to inform the next phases of intervention development and testing.

To explore group differences in improvements in electronically-monitored medication adherence to inform the next phases of intervention development and testing (Exploratory Aim 2), we will conduct longitudinal mixed effects models using Stata version 16.⁴⁹ Longitudinal trajectories of adherence will be estimated and tested for treatment group differences.

While this study is not designed to test for treatment-related differences in adherence by demographic or clinical variables, demographic (age, sex, race), clinical (side effects, diagnosis, additional adherence interventions), and psychosocial variables (parental involvement, emotional distress) previously associated with adherence¹⁰ (see Table 3) will be explored as potential covariates. Exploring the role of these variables as covariates will enhance the precision of our efficacy estimate. Data will also be disaggregated by sex in all publications to facilitate efforts to consider sex in the interpretation and generalization of findings.

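### Section 17.2 does not say how run-in adherence enters the Aim 2 mixed model; prespecifying the adjustment would stop chance imbalance from moving the arm difference

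*Combined protocol and SAP*

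**What the plan says.** Section 6.2.a makes four weeks of electronic monitoring an eligibility step: "AYAs must demonstrate < 95% adherence and use the electronic monitor without difficulty". It then says that "AYAs with < 95% run-in adherence will continue with study procedures". Criterion 8 in Table 5 (Section 10.1) excludes anyone at or above the cut-off. So every randomized AYA has a run-in value, and every value is below 95%.

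Section 9.1 gives the schedule as a "4-week run-in period, 1 week pre-treatment assessment, 8-week intervention or control group, and 4 week post-treatment period", 17 weeks in all. Section 6.2.a keeps the monitor in use throughout.

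Exploratory Aim 2 (Section 2.0) is "To explore group differences in improvements in electronically-monitored medication adherence". For the analysis, Section 17.2 commits to longitudinal mixed effects models and adds: "Longitudinal trajectories of adherence will be estimated and tested for treatment group differences". It does not name a baseline, a time origin, the weeks that count as outcome, or the contrast that measures the arm difference.

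The candidate covariates in 17.2 are age, sex and race; diagnosis, side effects and other adherence interventions; parental involvement and distress. They are to be explored, not fixed in advance, and the stated reason is a more precise efficacy estimate. Run-in adherence is not among them. No stratification of the randomization by run-in adherence is described.

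**The concern.** Improvement needs a pre-treatment reference, and the monitored run-in is the natural one. It is the same outcome, measured by the same device in the same people. Leaving its role open matters for two reasons.

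First, arms of 20 will differ in mean run-in adherence by chance. How far that difference carries into the estimated effect depends on the contrast chosen, and the reasonable contrasts carry it in opposite directions. Choosing after the data are seen would therefore matter.

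Second, the group was selected for low run-in values, so some of any rise within an arm is expected without an intervention effect.

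The stake is limited but real. Aim 2 exists to inform later development, and Section 7.1 says the data will inform a larger multi-site trial.

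**Working it through.** **Plan's own figures (Section 17.1).** 97 × (0.05 + 0.35) = 38.8, stated as 39. 97 − 39 = 58. 58 × 0.70 = 40.6, stated as 40. 40 × 0.80 = 32. All reproduce. No alpha, power, SD or effect size is given for Aim 2, so there is no power figure to check.

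**Inputs.** 20 per arm (Section 2.0). Share below the cut-off: "our preliminary data indicate that 71% of AYAs are non-adherent per electronic monitoring data" (Section 3.2). Assumed, because the document gives neither an SD nor a correlation: run-in adherence is normal before selection, and its correlation ρ with follow-up is 0.3 to 0.8. The unit is one SD of adherence before selection.

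**1. Selection.** Truncating a standard normal above its 71st percentile (z = 0.553) puts the mean 0.48 below the population mean. The remaining variance is 1 − 0.553 × 0.482 − 0.482² = 0.50, so the SD is 0.71.

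**2. Average effect of selection.** With no treatment effect, adherence rises by (1 − ρ) × 0.48 in both arms. In 6,000 simulated trials per setting, the mean arm difference stayed within 0.005 of 0 for follow-up-only, change and run-in-adjusted estimators. Type I error was 4.7-5.8%.

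**3. Chance imbalance.** The SD of the between-arm run-in difference is 0.71 × √(2/20) = 0.22. At 16 per arm it is 0.71 × √(2/16) = 0.25.

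**4. Shift from a 1-SD imbalance at 20 per arm.** Change: −(1 − ρ) × 0.22. Follow-up only: +ρ × 0.22. The last column is simulated.

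| ρ | Null rise, both arms | Change | Follow-up only | Run-in adjusted |
|---|---|---|---|---|
| 0.3 | 0.34 | −0.16 | +0.07 | 0.01 |
| 0.5 | 0.24 | −0.11 | +0.11 | 0.01 |
| 0.7 | 0.14 | −0.07 | +0.16 | 0.00 |
| 0.8 | 0.10 | −0.04 | +0.18 | 0.00 |

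The change and follow-up contrasts differ by the full imbalance, 0.22, at every ρ.

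**5. Weekly mixed models.** 3,000 simulated trials per setting at 20 per arm, with assumed intraclass correlation (ICC) and week-to-week autocorrelation 0.5. Shift per 1-SD run-in imbalance:

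| Role of run-in | ICC 0.3 | ICC 0.5 | ICC 0.7 |
|---|---|---|---|
| Omitted | +0.08 | +0.13 | +0.18 |
| Outcome, arm by period | −0.07 | −0.04 | −0.02 |
| Outcome, common run-in mean | −0.004 | −0.001 | +0.002 |
| Covariate | −0.005 | −0.001 | +0.003 |

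**6. Precision against change scores.** The change variance is proportional to (1 − ρ)² × 0.50 + (1 − ρ²). The adjusted variance is proportional to (1 − ρ²) × (1 + 1/36), where 1/36 allows for estimating the slope.
- ρ = 0.3: 0.91 × 1.028 / (0.245 + 0.91) = 0.81, and 1/0.81 = 1.23.
- ρ = 0.8: 0.36 × 1.028 / (0.02 + 0.36) = 0.97, and 1/0.97 = 1.03.

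The gain in effective sample size is therefore about 3-23%. The simulated SDs give slightly less: (0.313/0.340)² = 0.85 and (0.194/0.195)² = 0.99, or about 18% and 1%.

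In the weekly simulations, the SDs of the estimate at ICC 0.3 / 0.5 / 0.7 were:
- common run-in mean: 0.169 / 0.152 / 0.121
- arm by period: 0.183 / 0.159 / 0.123
- covariate: 0.193 / 0.176 / 0.143
- run-in omitted: 0.207 / 0.219 / 0.228

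So a single run-in covariate need not be more precise than a model of the whole series. Its main merit is that it removes the dependence on imbalance.

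**The case against.** The strongest reply is that absence from the covariate list does not mean absence from the model. Monitoring is one continuous series, and the run-in weeks may be the first points of the modelled trajectory. An outcome is not usually listed as its own covariate. This stands: a reader might infer that the plan leaves run-in adherence unadjusted, and the document does not establish that. But 17.2 does not state the opposite either. Using run-in weeks as outcome with free arm means still leaves a shift of 0.02 to 0.07; only the common-mean version removes it.

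Other stronger readings are tempting and should be resisted:

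- That regression to the mean biases the arm comparison. Randomization follows selection, so the expected rebound is the same in both arms. What remains is chance imbalance, in either direction.
- That run-in adherence is the plan's declared baseline. This is a reasonable inference, but no section says it.
- That adjustment gains a great deal of precision. The textbook ratio (1 − r²)/(2(1 − r)) gives 0.65 to 0.85 for r = 0.3 to 0.7, or 18-54% more participants. It assumes equal variances at run-in and follow-up, and selection below 95% cuts the run-in variance by about half.
- That the investigators intend to read within-arm gains as benefit. Section 17.2 tests group differences, and no passage plans a within-arm claim.
- That untreated adherence will rise overall. Section 5.1 refers to natural decline over about the intervention period, so the net direction is not established.

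**Conclusion.** The point holds as a free improvement to an exploratory analysis. Section 17.2 leaves the role of run-in adherence open, although the value is available for every randomized AYA. At 20 per arm, a typical chance imbalance moves the estimated arm difference by up to 0.16 SD under a change contrast or 0.18 SD under a follow-up-only contrast, with opposite signs. Adjustment brings this to about 0. There is no average bias and no meaningful inflation of type I error, and the precision gain over change scores is modest.

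The sizes rest on assumed correlations and a truncated normal distribution. Real adherence is bounded and skewed, so they indicate order of magnitude only. The primary enrollment endpoint and N = 40, which rests on the recruitment rate, are unaffected.

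**What to change.** In Section 17.2, under Exploratory Aim 2, prespecify one of two models:

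- (a) weekly adherence after randomization as outcome, with arm, time, arm-by-time and each AYA's run-in adherence as a fixed covariate; or
- (b) weekly adherence in all weeks, run-in included, as outcome, with the arms constrained to a common run-in mean.

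The two should not be mixed: (b) needs the run-in weeks as outcome data and (a) excludes them. Name the arm contrast and report the adjusted difference with a 95% CI. Add that within-arm change from run-in will not be interpreted as an intervention effect, because the selected group is subject to regression to the mean.

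The cost is a few sentences and, for (a), one degree of freedom. No new data, visits or participants are needed.
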